11.2. Continued Follow-up Discontinuation of Study Intervention

Describe efforts that will be made to continue follow-up of participants who discontinue the study intervention, but remain in the study for follow-up, especially for safety and efficacy study endpoints (if applicable). Reasonable efforts must be made to undertake protocol-specified safety follow-up procedures to capture adverse events (AE), serious adverse events (SAE), and unanticipated problems involving risks to subjects or others (UPIRSOs).

All patients that participate in the study, including those discontinued due to adverse reactions, will be followed until completion of the study or resolution of the adverse reaction (unless consent has been withdrawn).

12. Statistical Considerations

12.1. Statistical Hypotheses

State the formal and testable null and alternative hypotheses for primary and key secondary endpoints, specifying the type of comparison (e.g., superiority, equivalence or non-inferiority, dose response) and time period for which each endpoint will be analyzed.

Null hypothesis: a) No difference in % vital bone, % residual graft and % connective /other tissues between the groups.
b) No dimensional differences in alveolar ridge after ridge preservation between the groups.

12.2. Sample Size Determination

Include number of participants to recruit, screen, and enroll to have adequate power to test the key hypotheses for the study. Provide all information needed to validate your calculations and judge the feasibility of enrolling and following the necessary number of participants.

Using ANOVA, power analysis determined that we will be powered to find an overall difference among groups with 90% power if we enroll N=16/group (N=64) total. To account for attrition of 20%, an N=20 per group is needed. For post-hoc tests, this sample size will enable us to identify a difference of 15% bone (SD:15) between each of the groups 2-4 as compared to DFDBA particulate (group 1; control) with greater than 80% power. Because we also plan to do pairwise comparisons between groups, a larger N is desired. Thus, we will enroll 30 subjects per treatment group (120 total).

12.3. Populations for Analyses

Clearly identify and describe the analysis datasets (e.g., which participants will be included in each).

All study participants who complete the study intervention will be included in the analysis for all outcome measures.

12.4. Statistical Analyses

Include analysis of primary efficacy endpoints, secondary endpoints, safety analyses, and any planned interim analyses

The outcomes of the histologic and clinical parameters will be summarized with the sample size, mean, standard deviation, median, minimum and maximum. ANOVA will be used to determine differences between the 4 groups. Post-hoc tests will be performed to determine differences between the DFDBA particulate group (Group 1 – active control) and the other 3 groups. Pairwise comparisons between groups will be assessed with two-sample t-testing. The significance of variation in the group effect with another variable will be assessed with an interaction term in a linear model. All statistical testing will be two-sided with a significance level of 5%. Spearman rank and Pearson correlations between clinical parameters and histologic parameters will be analyzed as well. All statistical analyses will be done with statistical software.

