3.1. Objective(s) Clearly and concisely define the primary and secondary outcomes.	3.2. Endpoint Clearly define the endpoints. (endpoints are the basis for concluding that the objective has been met).	3.3. Justification for Endpoint Briefly explain why the endpoint(s) were chosen.
Primary Histologic Outcome	% vital bone formation	% vital bone formation shows the amount of new bone formed after the procedure. The higher this % is the better the healing of the site
Secondary histologic outcomes	% residual graft material, and % "CT/other" (fibrous tissue and marrow space)	% residual graft material shows how much of the graft material remained intact. Ideally all the graft materials should turn over to vital bone % CT/other (fibrous tissue and marrow space) is the amount of tissue that is neither native bone or graft material. It may be connective tissue that will mature to osteoid and bone or marrow space that is part of the normal healing
Secondary Clinical outcomes	Change in ridge width; Change in buccal ridge height; Change in lingual ridge height	Clinical measurements show effects of procedures on dimensional changes in the alveolar ridge during healing

4. Rationale

Briefly state the reason for conducting the clinical trial.

Allografts and xenografts are commonly used in ridge preservation procedures. Demineralized freeze-dried bone allografts (DFDBA) are available in particulate and fibers forms. Newer products on the market combine xenografts and DFDBA, but there are little data on histologic healing. Our group is known for this type of research, and we wish to determine if DFDBA fibers result in similar or different histologic outcomes than DFDBA particulate, and whether bovine-derived xenograft combined with DFDBA fibers result in similar or different histologic outcomes than xenograft combined with DFDBA particulate. Finally, we will be able to assess histologic outcomes when particulate DFDBA is used alone versus when it is combined with xenograft and when DFDBA in fiber form is used alone versus when it is combined with xenograft.

5. Study Design

5.1. Number of Groups/Arms	4	Group name(s)	
 1. Group 1: DFDBA particulate at 125-850 micron size (Vallos) 2. Group 2: Xenograft (Bio-Oss) combined with DFDBA particulate at 125-850 micron size (Vallomix) 3. Group 3: DFDBA fibers (Vallos-F)
-----------------------------------	---	----------------------	---

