All of the bone graft material and overlying membrane material will be provided by Geistlich Biomaterials. To eliminate variability that might occur if more than one human donor's tissue is used in the study, all of the DFDBA graft material for all treatment groups will be derived from a single human donor. The DFDBA graft material will be tested for inductivity by the tissue bank (DCI Donor Services Tissue Bank).						
All patients will have a single non-molar tooth extracted. Following extraction, patients will be randomized to one of the 4 treatment groups. Clinical ridge measurements will be made using a custom-made thermoplastic measurement stent, and ridge preservation will be performed using one of the materials listed above, per assigned study arm. After graft placement, the graft material will be covered with a resorbable collagen membrane (Bio-gide) membrane (Geistlich Biomaterials) and the site will be sutured with resorbable sutures without attempt at primary closure.						
Patients will return 1 to 3 weeks after ridge preservation for post-operative evaluation, and thereafter as indicated by clinical findings. Following the 18 to 20-week wound healing period, a core biopsy will be harvested from the site at the time of implant placement. Just prior to the core biopsy, clinical ridge measurements will again be made using the customized measurement stent.						
The core biopsy will be evaluated histomorphometrically for the primary outcome: % vital bone formation. Secondary histologic outcomes include % residual graft material and % "CT/other" (fibrous tissue and marrow space). The histomorphometric						

evaluation will be performed blindly, as the cores being examined will be de-identified as to study arm. In line with our other studies, we will also evaluate the following **secondary clinical outcomes** for each subject: change in ridge width; change in buccal ridge height and change in lingual ridge height.

DETAILED DESCRIPTION OF METHODS:

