the bony crest. Prior to tooth extraction, the clinical measurement stent will be placed and measurements of ridge width and ridge height will be taken and recorded to the nearest 0.5mm. Ridge width will be measured to the nearest 0.5mm using a ridge caliper at a point **approximately 3mm apical to the facial and lingual bony crest** through small holes created in the stent at those locations. Ridge height will be measured to the nearest 0.5mm through two holes in the occlusal aspect of the stent – one hole directly above the facial bony crest and another hole directly above the lingual bony crest. This stent will be retained for use during the subsequent implant placement surgery.

Use of the stent and subsequent measurements are for research purposes, not standard care.

Tooth extraction will be performed as atraumatically as possible. Following tooth extraction, a final determination of enrollment into the study will be conducted based on the integrity of the buccal bone wall plate at the extraction site. If the buccal plate is intact, defined as **no bony dehiscence greater than 50% of the socket depth**, the patient will remain enrolled in the study. Conversely, if the buccal plate integrity has not been maintained (bony dehiscence >50%) the patient will be exited from the study and standard care therapy will be delivered to the patient.

After extraction, the number of bony walls in each socket will be recorded along with the presence of any bony dehiscences or fenestrations. Buccal and lingual flap elevation will be minimized and will extend no more than 2-3mm beyond the bony crest on the facial and lingual surfaces. The buccal plate thickness will be measured using an Iwanson gauge positioned perpendicular to the inner wall of the extraction socket. One beak of the gauge will be placed within the extraction socket 1.0mm apical to the alveolar bone crest. The other beak will be placed on the external bone surface 1.0mm apical to the alveolar bone crest. This buccal plate thickness measurement will be recorded to the nearest 0.1 mm. Measurements taken with the Iwanson gauge are for research purposes, not standard care.

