The socket will be thoroughly debrided, the patient will be randomized to one of the study groups (Group 1, 2, 3 or 4), and the graft material will be placed in the extraction socket to a level even with the interproximal bone height of the mesial and distal aspects of the socket. The material will be condensed into the socket gently. In all sockets, a BioGide resorbable collagen membrane will be placed over the socket and graft material to retain the material in place. The edges of the membrane will be “tucked” under the flap margins to help with membrane retention, and the flaps will be sutured. Primary closure of the flaps will not be performed, per standard care. Flaps will be stabilized with chromic gut sutures, per standard care.

Visit 3 - Post-operative visit

The post-operative visit after extraction/ridge preservation will be scheduled approximately 3 weeks (± 1 week) after the procedure. At this visit a clinic exam will be performed to evaluate healing. Any remaining sutures will be removed. If needed, an optional POT visit may be scheduled before this visit, per standard care and as determined by patient need.

Visit 4 - Pre-implantation:

Approximately 3-4 months after the extraction, the patient will be seen for pre-implant evaluation, per standard care. If needed, a cone beam computed tomography (CBCT) scan will be taken per standard care.

Prior to surgery, pregnancy status will be confirmed verbally. An over-the-counter pregnancy test will be provided if pregnancy status is unknown or suspected (research). A negative result is required to continue being in the study.

Visit 5 - Implant placement:

Prior to surgery, pregnancy status will be confirmed verbally. An over-the-counter pregnancy test will be provided if pregnancy status is unknown or suspected (research). A negative result is required to continue being in the study.

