Randomization of subjects is done through use of envelopes inside which is a piece of paper with the group to which the subject will be assigned. 30 envelopes will be prepared for each of the 4 groups. The envelopes will be sealed and shuffled. The faculty staffing the procedure will draw an envelope from the stack prior to the surgical procedure appointment. Since the outcome of the study is the histologic healing, blinding of the surgeon is not necessary.
Blinding is performed only for histomorphometric measurements. The person doing histomorphometric analysis is blinded as to study group.
10.2. Study Intervention Compliance Define how adherence to the protocol (e.g., administration of study intervention, use of device,) will be assessed, and verified (if applicable, e.g., plasma assays, electronic monitoring devices, daily diaries).
Patients will need to be present at each scheduled visit. Failure to attend visits will result in exit from the study. All providers placing study materials as part of the study intervention will be trained and provided with detailed instructions to ensure methods are consistent and in compliance with the protocol. All faculty staffing residents are familiar with the study protocol and can verify the results of the procedure and measurements taken.
10.3. Permitted Concomitant Therapy This section should be consistent with the medication restrictions in the inclusion/exclusion criteria previously listed. Describe how allowed concomitant therapy might affect the outcome (e.g., drug-drug interaction, direct effects on the study endpoints).
N/A
10.4. Rescue Medicine List all medications, treatments, and/or procedures that may be provided during the study for "rescue therapy" and relevant instructions.
N/A, no rescue medicine

11. Study Intervention Discontinuation
11.1. Discontinuation of Study Intervention Describe the criteria for discontinuing the study intervention (e.g., halting rules), including any monitoring test(s) and associated clinical decision point(s). Include reasons for temporary discontinuation of the study intervention (e.g., type and quantity of adverse events), clearly stating the length of time, if applicable, and describe the data to be collected at the time of study intervention discontinuation and approaches for restarting administration of or re-challenging with study intervention.

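### Change in ridge width is compared without adjusting for the baseline width already recorded, which probably gives up some precision

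*Combined protocol and SAP*

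**What the plan says.** The secondary clinical outcomes in section 3 are "Change in ridge width; Change in buccal ridge height; Change in lingual ridge height". The null hypotheses in section 12.1 include one of no difference between groups in ridge dimensions.

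Section 12.4 covers histologic and clinical parameters together. For the overall comparison, "ANOVA will be used to determine differences between the 4 groups". Post-hoc tests then compare Group 1 with the other three groups, and "Pairwise comparisons between groups will be assessed with two-sample t-testing". No covariate is named for any of these. The one linear model in the section has another purpose: "The significance of variation in the group effect with another variable will be assessed with an interaction term in a linear model". The other variable is not identified.

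The baseline exists. Under Visit 2 in section 5.3, "Prior to tooth extraction, the clinical measurement stent will be placed and measurements of ridge width and ridge height will be taken", to the nearest 0.5 mm. At Visit 5 the same stent is used to measure width again at the same locations.

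**The concern.** A change score subtracts the whole baseline value, which amounts to fixing the coefficient of baseline on follow-up at 1. Unless the true coefficient happens to be 1, change remains correlated with baseline. Chance differences in baseline width between arms then add noise to the group comparison. A model containing baseline estimates that coefficient and removes the noise.

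The interaction model in section 12.4 does not do this. It asks whether the group effect varies with some other variable; it is not a baseline-adjusted comparison of the groups.

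At stake is the precision of the ridge-width comparisons. The lost precision is already contained in the ANOVA standard error, so it is a single loss and not an added bias. The trial is sized on % bone (section 12.2), and no power is stated for ridge width. The primary outcome and the sample size are unaffected.

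**Working it through.** **Inputs from the documents.** Four arms, 30 enrolled per arm, 20% attrition (section 12.2); two-sided 5% level (section 12.4). Section 12.2's own attrition step reproduces: 16/(1 − 0.20) = 20 per group. It gives no figure for ridge width. Applying the same attrition to planned enrollment gives 30 × 0.80 = 24 completers per arm, 96 in all, and 96 − 4 = 92 residual degrees of freedom for the ANOVA.

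**Assumed inputs.** The baseline/follow-up correlation r and the SD ratio k (follow-up SD = k × baseline SD s) are not in the documents. Ranges used: r = 0.5 to 0.9; k = 0.8, 1.0, 1.2.

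**Step 1: error variances.**

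- Change score: s²(1 + k² − 2rk).
- Model with baseline: k²s²(1 − r²).
- Difference: s²(1 − 2rk + r²k²) = s²(1 − rk)². This is never negative, and it is zero only when rk = 1.

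**Step 2: variance ratio, adjusted over unadjusted.** With k = 1 this reduces to (1 − r²)/(2(1 − r)) = (1 + r)/2.

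| k | r = 0.5 | r = 0.7 | r = 0.9 |
|---|---|---|---|
| 0.8 | 0.48/0.84 = 0.571 | 0.3264/0.52 = 0.628 | 0.1216/0.20 = 0.608 |
| 1.0 | 0.750 | 0.850 | 0.950 |
| 1.2 | 1.08/1.24 = 0.871 | 0.7344/0.76 = 0.966 | 0.2736/0.28 = 0.977 |

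At k = 1.2 and r = 0.8, where rk = 0.96, the ratio is 0.5184/0.52 = 0.997. Over the grid it runs from 0.57 to 1.00.

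**Step 3: pay for the covariate.** Estimating one slope inflates the contrast variance by about 1 + 1/90 and moves the t quantile from 92 to 91 degrees of freedom, a factor of 1.00015. The ratio of 95% interval widths for a pairwise contrast, both taken from the four-group model, is √(variance ratio × (1 + 1/90)) × 1.00015. At k = 1:

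- r = 0.5: √(0.75 × 1.0111) × 1.00015 = 0.871, or 13% narrower.
- r = 0.7: √(0.85 × 1.0111) × 1.00015 = 0.927, or 7% narrower.
- r = 0.9: √(0.95 × 1.0111) × 1.00015 = 0.980, or 2% narrower.
- Worst case, rk = 1: √1.0111 × 1.00015 = 1.006, or 0.6% wider.

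Simulation at 24 per arm agreed to within 0.001 at each of the three correlations.

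**Step 4: the same gain as power.** With k = 1, a contrast that has 80% power unadjusted would have 89.6%, 85.6% or 81.5% at r = 0.5, 0.7 or 0.9.

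**Order of measurement and allocation.** The covariate is safest if recorded before the arm is known. The documents disagree on this:

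- Section 5.3, Visit 2, measures before extraction and randomizes later: "The socket will be thoroughly debrided, the patient will be randomized to one of the study groups".
- The summary earlier in section 5.3 has the reverse order: "Following extraction, patients will be randomized to one of the 4 treatment groups. Clinical ridge measurements will be made".
- Section 10.1 places allocation earlier still: "The faculty staffing the procedure will draw an envelope from the stack prior to the surgical procedure appointment".

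The surgeon is not blinded (section 5.3). Under section 10.1, baseline width could therefore be read with the arm known.

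**The case against.** **It is an improvement and not an error.** An unadjusted change score is a legitimate analysis with valid type I error, and ridge width is one of three secondary clinical outcomes. This stands, and the point claims no more.

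**The gain rests on assumed numbers.** Neither r nor k is in the documents. At k = 1.2 the interval-width ratios are about 0.94, 0.99, 1.00 and 0.99 at r = 0.5, 0.7, 0.8 and 0.9, so little is gained over much of that row. The 13% figure is also a favorable end of the equal-SD case: r = 0.5 with equal SDs means that change varies as much between patients as baseline width does, since s²(2 − 2 × 0.5) = s². Measuring with the same stent at the same locations makes a higher r plausible. This also stands, and it is why the result is a range that includes zero. What tips the balance is asymmetry: the possible loss is 0.6% of interval width.

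**The comparator is not the planned t-test, and the plan promises no intervals.** The figures in step 3 compare two four-group models, which isolates the covariate. A separate t-test has 24 + 24 − 2 = 46 degrees of freedom and a t quantile of 2.013, against 1.986 on 91. With equal variances across arms, even the worst case comes to √1.0111 × 1.986/2.013 = 0.99 of the planned t-test's width. That extra comes from pooling the error variance and should not be credited to the covariate. Interval width here stands for precision generally; the same ratios govern the tests.

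**Heights would stay unadjusted.** True, and the plan would then be mixed. Height is read through holes in the occlusal aspect of the stent, and the documents do not show that this gives a baseline level worth adjusting for. No gain is claimed there, nor for buccal plate thickness, dehiscence or % vital bone.

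**Allocation timing is a separate matter.** Partly so: baseline width already enters the planned change score, so the conflict matters under either analysis. It is raised here because the covariate should precede knowledge of the arm, and it adds nothing to the size of the efficiency loss.

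**Conclusion.** The point holds as an efficiency weakness in one secondary outcome. The planned comparison of change in ridge width is valid but leaves out a baseline measured in every patient whose change can be computed. With equal SDs and 24 completers per arm, adjustment would narrow pairwise 95% intervals by 2% to 13% for r between 0.9 and 0.5. With unequal SDs the gain could be larger or vanish, and the cost is at most 0.6% of interval width. These sizes rest on assumed values of r and k and on 20% attrition. The direction does not, apart from that small cost when rk is close to 1.

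**What to change.** In section 12.4, specify that change in ridge width is analyzed with a linear model containing group and baseline ridge width. Take the overall test and the pairwise contrasts from that model, with 95% confidence intervals. Keep the unadjusted ANOVA as a sensitivity analysis, which also preserves comparability with the group's earlier studies. Settle this before results are seen, because adjustment added afterwards is open to challenge.

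Reconcile sections 5.3 and 10.1 into one statement of the order of measurement and allocation, so that baseline width is recorded before the assignment is known.

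The cost is wording in section 12.4, the reconciled statement, and 1 of 92 residual degrees of freedom. No new data are needed. No patient is lost to a missing covariate, because the change itself cannot be computed without the baseline.

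### Pairwise t-tests at an unadjusted 5%: over six pairs, about a 20% chance of a false difference on % vital bone (no ANOVA gate, all products equal), or about 12% behind a gate when one product differs by 15 points

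*Combined protocol and SAP*

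**What the plan says.** Section 12.4 describes three layers of testing for the histologic and clinical outcomes.

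- A four-group ANOVA.
- Comparisons with the control: "Post-hoc tests will be performed to determine differences between the DFDBA particulate group" (Group 1) and the other three groups. The procedure is not named.
- In a separate sentence, "Pairwise comparisons between groups will be assessed with two-sample t-testing". The pairs are not listed.

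The level is common to all of them: "All statistical testing will be two-sided with a significance level of 5" (per cent). No adjustment for multiple comparisons appears anywhere, and nothing makes the second or third layer depend on the ANOVA.

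Section 12.2 treats the pairwise comparisons as planned, and as the reason for going beyond 20 per group: "Because we also plan to do pairwise comparisons between groups, a larger N is desired". Enrolment is then set at 30 per group.

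Section 4 (Rationale) asks four product questions: 1 vs 3, 2 vs 4, 1 vs 2 and 3 vs 4. The second is "whether bovine-derived xenograft combined with DFDBA fibers result in similar or different histologic outcomes than xenograft combined with DFDBA particulate"; the last is the comparison "when DFDBA in fiber form is used alone versus when it is combined with xenograft".

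**The concern.** Four groups make six pairs. If each pair is tested at 5%, the chance of at least one false difference is well above 5%. The unnamed post-hoc procedure might be an adjusted one, but it covers only 1 vs 2, 1 vs 3 and 1 vs 4. The questions 2 vs 4 and 3 vs 4 are left to the plain t-tests.

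The trial asks whether four marketed products heal similarly or differently, so a false difference is a wrong statement about a named product. Reading an ANOVA gate into the plan helps only in part. It protects when all four products are equal. Once one product truly differs, the ANOVA is nearly always significant and the three equal products are compared with no further control.

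**Working it through.** **Inputs.** Four groups; two-sided 5% (12.4); difference 15 points, SD 15, so d = 1; attrition 20%; 30 enrolled per group (12.2). Evaluable per group: 30 × (1 − 0.20) = 24. Normal data and equal SDs are assumed unless stated.

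**The plan's own figures.** The documents give no family-wise error rate, so only the sample size can be reproduced. For one unadjusted two-group comparison at 80% power, n = 2 × (1.96 + 0.84)² × (15/15)² = 15.7, so 16 per group; 16/0.80 = 20. This matches 12.2. Power at 16 is 80.7% by the normal approximation and 78.1% by noncentral t; at 20 it is 86.9% by noncentral t. The stated size therefore matches an unadjusted test.

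**Ungated, all four products equal.** With a pooled SD, at least one of six tests is significant when the studentized range of four means exceeds √2 × t(0.975; 92) = √2 × 1.986 = 2.81. That probability is 20.1%. Simulated two-sample t-tests give 20.2% to 20.5%. The result hardly depends on n (19.8% to 20.5% for 16 to 30 per group). Treating the tests as independent would overstate it: 1 − 0.95⁶ = 26.5%.

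By set of pairs (simulation, 24 per group):

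| Pairs tested | Chance of at least one false difference |
|---|---|
| All six | 20.2% |
| Five named in the documents (the four Rationale pairs plus 1 vs 4) | 18.1% |
| Four Rationale pairs | 16.0% |
| Three Group 1 pairs | 12.5% |
| 2 vs 4 and 3 vs 4 only | 9.0% |

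**Behind a 5% ANOVA gate, six pairs, 24 per group.**

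- All equal: 5.0%.
- One product shifted by 15 points: the ANOVA noncentrality is 96 × 0.1875 = 18, and the gate opens in 95% of trials. Three equal products remain, with three null pairs. The error is 12.1% to 12.2%.
- One product shifted by 0.5 SD: the gate opens in about 38%, and the error is about 9%.
- Two products 15 points from the other two: 9.8%.

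**With adjustment, 24 per group.**

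- Tukey over six pairs: 5.0% with all equal, 2.8% with one product shifted by 15 points.
- Holm over the five named pairs: 4.2% and 3.6% to 3.8%. The like-for-like unadjusted figure, with all equal, is 18.1%.

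**Power per pair at d = 1.** The noncentrality is √(n/2), which is 3.464 at n = 24. The Tukey critical value there is 2.617 on 92 df.

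| Evaluable per group | Tukey | Unadjusted two-sample t |
|---|---|---|
| 16 | 57.6% | 78.1% |
| 20 | 70.3% | 86.9% |
| 22 | 75.5% | 90.0% |
| 24 | 79.9% | 92.4% |
| 25 | 81.9% | 93.4% |
| 30 | 89.5% | 96.8% |

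Holm over five, simulated: 79.5% to 81.8% at 24 and 89.5% to 91.2% at 30, depending on which products differ.

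**Sensitivity to unequal SDs** (10/10/20/20, an assumption not taken from the documents; 24 per group, equal means): Tukey 6.4%, Games-Howell 4.9%, ungated t-tests 19.7%. Under equal SDs, Games-Howell power per pair at 24 is 78.2%.

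**The case against.** The strongest reply has four parts.

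- **The family is not fixed at six.** The pairs are not listed, and 2 vs 3 is covered only by the general phrase about comparisons between groups. This stands as a reason to give a range. Six pairs is still the natural reading of an unrestricted sentence, and every narrower set shown above exceeds 5%.
- **The gated 12% is near the top of its range.** It needs a shift of about 15 points. With a smaller shift, a two-versus-two pattern or only the four Rationale pairs, the figure is 9% to 10%. This is correct. But 15 points is the plan's own design effect, and 9% to 10% is still about double the nominal level.
- **The overall null hypothesis on vital bone is tested once, by one ANOVA at 5%.** That test is not inflated, and the trial is post-approval with superiority unticked. How strictly to control follow-on comparisons is partly a matter of judgement. However, the Rationale's questions are pairwise, and section 12.2 sizes the trial for them.
- **Group 1 is the named control, so Dunnett would fit better than Tukey.** For the three Group 1 pairs it gives 85.7% power at 24 evaluable and 93.0% at 30. It leaves 2 vs 4 and 3 vs 4 uncovered, and they would need their own adjusted test. It is a possible component, not a full remedy.

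**Conclusion.** The concern holds and should be fixed before analysis. For % vital bone, following section 12.4 as written gives about a 20% chance of at least one false difference if all six pairs are tested without a gate and the products are equal, and 9% to 18% for narrower sets. If a significant ANOVA is required first, the chance is 5% with all products equal and about 12% with one product 15 points away. These figures assume normal data, equal SDs and 24 evaluable per group. The ungated all-equal rates do not depend on the common SD, and the error rates are almost the same at 30 per group, so more patients would not cure this. For the Group 1 comparisons the defect is an unspecified procedure. For the t-tests it is a stated unadjusted level.

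**What to change.** In section 12.4, replace the post-hoc and t-test sentences with wording such as:

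> For each histologic and clinical outcome, all six pairwise differences between groups, including the three with Group 1, will be tested by the Tukey-Kramer procedure at a family-wise two-sided 5% within that outcome. The ANOVA is reported as the overall test and does not gate them. % vital bone is the primary outcome; all others are secondary, with no adjustment across outcomes.

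If Holm over a listed set is preferred, the list must hold the four Rationale pairs and 1 vs 4. If unequal variances are expected, name Games-Howell in advance.

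In section 12.2, state the matching power for 15 points, SD 15: Tukey 79.9% per pair at 24 evaluable per group and 89.5% at 30.

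The change is to wording only; no extra patients are needed. The cost is power per pair, 79.9% against 92.4% at 24. Section 12.2 promises power "between each of the groups 2-4 as compared to DFDBA particulate (group 1; control) with greater than 80% power". At exactly 20% attrition Tukey falls just short of that. It passes 80% from 25 evaluable per group, that is, attrition up to (30 − 25)/30 = 16.7%. At the 16 evaluable or 20 enrolled per group beside which the promise is made, Tukey would give 57.6% or 70.3%, so the promise should be restated for the 30 actually enrolled.

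### Section 12.4 does not say how treatment arm is handled in the clinical–histologic correlations; pooled over four arms, they can create, mask or reverse the relation among patients on the same graft

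*Combined protocol and SAP*

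**What the plan says.** The correlations rest on one sentence in section 12.4: "Spearman rank and Pearson correlations between clinical parameters and histologic parameters will be analyzed as well". It does not say whether they are computed over all patients, within each arm, or after adjustment for arm.

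The clinical outcomes listed in section 3 are "Change in ridge width; Change in buccal ridge height; Change in lingual ridge height". The histologic outcomes there are % vital bone, % residual graft and % CT/other. Section 12.4 does not define which clinical parameters enter the correlations.

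Elsewhere in the same paragraph, group is named wherever it is meant to enter: the ANOVA, the post-hoc tests against Group 1, the pairwise t-tests, and this sentence: "The significance of variation in the group effect with another variable will be assessed with an interaction term in a linear model". That last sentence names neither the variable nor the outcome and is not linked to the correlations. Section 12.3 sets a single analysis population for every outcome, and 12.4 applies a two-sided 5% level to all testing.

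**The concern.** A correlation computed over all four arms has two parts: how the arm means of the two outcomes line up, and how the outcomes move together among patients given the same graft. The arms were chosen because their histology may differ (section 4), and hypothesis (b) in section 12.1 concerns ridge differences between the same arms. If a material shifts both outcomes, the first part can appear as an association that no single arm shows. It can also hide or reverse one that every arm shows.

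At stake is a secondary statement, for example that sites with more vital bone keep their ridge dimensions better. A pooled coefficient with a 5% test could support or deny that statement merely because of the graft means.

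**Working it through.** **Inputs from the documents.** Section 12.2 plans on a 15-point difference with SD 15: "this sample size will enable us to identify a difference of 15% bone (SD:15) between each of the groups 2-4", compared with Group 1. That is 15/15 = 1 SD. The same section starts from "90% power if we enroll N=16/group (N=64) total", then "To account for attrition of 20%, an N=20 per group is needed", and finally enrolls 30 per group. Applying the plan's 20% attrition to 30 leaves 24 per arm, so N = 96.

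**The plan's own figures.** 16/(1 − 0.20) = 20 reproduces. For the 1 SD contrast at 16 per group, √(16/2) − 1.96 = 0.868, a power of 80.7% by normal approximation (78.1% by t). At 20 per group the power is 88.5% (86.9% by t). The stated power above 80% is therefore reproduced for an unadjusted comparison, and 1 SD is a fair scale for vital bone. The plan states no figure for the correlations.

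**Inputs that are assumed.** The documents give neither an arm effect nor an SD for ridge change. A range of 0 to 1 SD is used. The true correlation within each arm is set to 0 unless stated.

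**Formula.** With equal arms and outcomes in within-arm SD units, let C be the average product of the centered arm means, Va and Vb their variances (divisor 4), and ρw the within-arm correlation:

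pooled ρ = (C + ρw) / √[(1 + Va)(1 + Vb)]

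- Two against two, 1 SD on both: centered means ±0.5, so C = Va = Vb = 0.25; 0.25/1.25 = 0.20.
- One against three, 1 SD on both: centered means −0.75 and three of 0.25, so C = Va = Vb = (0.5625 + 3 × 0.0625)/4 = 0.1875; 0.1875/1.1875 = 0.16.
- Two against two, 1 SD vital bone and 0.5 SD ridge: 0.125/√(1.25 × 1.0625) = 0.11.
- Two against two, 0.5 SD on both: 0.0625/1.0625 = 0.06.
- Form shifts vital bone, xenograft shifts the ridge, 1 SD each: the centered products are +0.25, −0.25, −0.25, +0.25, so C = 0 and ρ = 0.
- Effect on one outcome only: C = 0 and ρ = 0.

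**Chance of a significant pooled Pearson test**, by simulation with normal data and ρw = 0:

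| Pattern of arm effects | Pooled r | N = 96 | N = 120 |
|---|---|---|---|
| 1 SD both, two vs two | 0.20 | about 51% | 60% |
| 1 SD both, one vs three | 0.16 | about 34% | 42% |
| 1 SD and 0.5 SD, two vs two | 0.11 | about 18% | 22% |
| 0.5 SD both, two vs two | 0.06 | about 9% | 10% |
| Different factors | 0.00 | 5% | 5% |
| One outcome only | 0.00 | 5% | 5% |

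A hand check of the first row at N = 96: atanh(0.20) × √93 = 0.2027 × 9.644 = 1.955, against a critical value of 1.96, so about 50%. A second simulation gave values within about one point of the first three rows at N = 96. Spearman stays within 3 points of Pearson throughout, so reporting both gives no protection.

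**Masking and reversal.** With ρw = 0.4 and 1 SD effects along different factors, the pooled value is 0.4/1.25 = 0.32. With ρw = 0.2 and opposed 1 SD effects, two against two, it is (−0.25 + 0.2)/1.25 = −0.04.

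**After removing arm means.** The Pearson correlation of arm-centered values, tested on N − 2 − 3 degrees of freedom, averages 0.00 and rejects in 4.7% to 5.4% of trials in every pattern, at N = 96 and N = 120. The arm-adjusted Spearman version was not simulated.

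**The case against.** The strongest reply is that the plan is silent here, and silence is not a decision to pool. That stands: within-arm correlations would also fit the sentence. But an analyst following 12.4 and 12.3 as written would use all completers together, and nothing in the text would stop that.

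A reader might infer that any graft effect on both outcomes produces a false correlation. The documents do not support this. The arms cross form (particulate or fiber) with xenograft (with or without), and effects along different factors produce none. The arm means must covary.

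The size can also be challenged, and rightly. The plan's 1 SD applies to vital bone only and to contrasts with Group 1. The closest pattern is one against three, which gives about 34% rather than 51%, and even that needs an assumed 1 SD ridge effect. With half an SD on both outcomes, the excess over 5% is small.

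A correlation across all sites regardless of material is a legitimate description, and the plan does not say that the within-arm relation is its target. That stands too; the pooled test misleads only when read as a statement about patients on the same graft. Nor is a within-patient relation at issue, since each subject gives one site. Finally, if clinical parameters include measures taken before grafting, such as buccal plate thickness, the graft cannot shift them and the mechanism does not arise.

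**Conclusion.** The point holds as a free improvement. The plan leaves the handling of arm open, and the default reading gives pooled coefficients whose meaning depends on how four arm means line up. Across the assumed range, the chance of a significant pooled result with no within-arm relation runs from the nominal 5% to about half of trials at N = 96. The upper end needs effects of 1 SD on both outcomes, aligned two against two. These figures rest on normal data, equal arms, 20% attrition and an arm effect on ridge change that the documents do not supply.

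A reader might go further and take this as a threat to the trial's main result. It is not. The correlations belong to no listed objective, hypothesis or sample-size claim, and the ANOVA on vital bone does not use them.

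**What to change.** In 12.4, state that correlations between the ridge changes and the histologic outcomes will be partial correlations given treatment group, in Pearson and Spearman form, with error degrees of freedom reduced by 3. Show the four within-arm coefficients beside each one as description only; with about 24 patients per arm their 95% limits are roughly ±1.96/√21 = ±0.43 on the Fisher scale. Name the clinical parameters meant. If they are the three ridge changes, label the 3 × 3 × 2 = 18 coefficients exploratory.

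The cost is one sentence, a small change to the code, and 3 degrees of freedom (94 to 91 at N = 96). It needs no new data and no change to the sample size.
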